- ^c Biomarkers will be assessed via blood draws at Week 1 (pre-dose Day 1), Week 3 (pre-dose Day 15), and at timepoints noted from Weeks 12 through 52. Biomarkers will also be assessed via LP in CSF before the first dose of ocrelizumab and from a second LP at either Week 12, 24, or 52 following the first dose of ocrelizumab.

[figure not shown]
Figure 2 Study Schema: RMS Cohort Arm 4

CSF = cerebrospinal fluid; LP = lumbar puncture; RMS = relapsing multiple sclerosis.

- ^a In the control arm (Arm 4), treatment with ocrelizumab will be delayed for 12 weeks to follow the first and second CSF collection, separated by 12 weeks. Ocrelizumab will then be administered at Weeks 1, 3, 24, and 48. The first dose will be administered as two infusions of 300 mg given on Day 1 and Day 15. The subsequent doses will be given as single 600-mg infusions.
- ^b The Safety Follow-up Period will begin only if the patient discontinues from treatment early or completes the study and does not continue on ocrelizumab treatment (i.e., commercially available or from another source). Patients will be assessed in safety follow-up every 24 weeks for 48 weeks following the last infusion of ocrelizumab. After 48 weeks, if the peripheral blood B-cell count remains depleted, monitoring of the patient should continue at 24-week intervals until the B-cell count has returned to the baseline value or to the lower limit of the normal range, whichever is lower.
- ^c Biomarkers will be assessed via blood draws at Weeks -12, 1 (pre-dose Day 1), 3 (pre-dose Day 15), and at timepoints noted from Weeks 12 through 52. Biomarkers will also be assessed via LP in CSF, in two LPs separated by a 12-week interval, before administration of the first dose of ocrelizumab. Patients in this arm will be asked if they are willing to give an optional CSF sample via LP 12 weeks after the ocrelizumab dose.

Figure 3 Study Schema: PPMS Cohort

CSF = cerebrospinal fluid; LP = lumbar puncture; PPMS = primary progressive multiple sclerosis.

- ^a For the PPMS cohort, ocrelizumab 600 mg will be administered as two 300-mg IV infusions separated by 14 days at a scheduled interval of every 24 weeks.

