2.2.2 Exploratory Endpoints

The exploratory endpoints for RMS Arm 4 include:

Change from first LP to second LP comparing Arm 4 to Arm 1 in:

- Levels of NfL in CSF
- Number of CD19 + B cells in CSF

- Number of CD3 + T cells in CSF
- Levels of NfL in blood
- Number of CD19 + B cells in blood
- Number of CD3 + T cells in blood

The exploratory endpoints for the PPMS cohort are:

- Change in levels of NfL in CSF from treatment baseline to post-treatment
- Change in number of CD19 + B cells in CSF from treatment baseline to post-treatment
- Change in number of CD3+T cells in CSF from treatment baseline to post-treatment

For both RMS and PPMS cohorts, other exploratory endpoints include the impact of ocrelizumab treatment on other CSF biomarkers, blood biomarkers and MRI biomarkers listed in this section.

Change from treatment baseline in CSF biomarkers:

- %CD19+ B cell
- %CD3+ T cell
- %CD4+ (CD3+)
- CD4+CD3+ number
- %CD4- (CD3+)
- CD4-CD3+ number
- %IgD+CD27+ (CD19+)
- IgD+CD27+CD19+ number
- %IgD+CD27- (CD19+)
- IgD+CD27-CD19+ number
- %IgD-CD27- (CD19+)
- IgD-CD27-CD19+ number
- %IgD-CD27+ (CD19+)
- IgD-CD27+CD19+ number
- %CD138+CD38+ (IgD-CD27+)
- CD138+CD38+IgD-CD27+CD19+ number
- %CD138-CD38- (IgD-CD27+)
- CD138-CD38-IgD CD27+CD19+ number
- %CD138-CD38+ (IgD-CD27+)
- CD138-CD38+IgD-CD27+CD19+ number
- %CD38+ (IgD+CD27-)
- CD38+IgD+CD27-CD19+ number
- IgG
- IgM
- CXCL13
- CCL19
- Strem2

- YKL40
- IL-6

Change from treatment baseline in Blood biomarkers:

- %CD19+ B cell
- %CD3+ T cell
- CD3+ T cell number
- CD4+T cell number
- CD8+T cell number
- CD19+ B cell number
- CD56+CD16+ NK cell number
- CD4/CD8 Ratio
- NfL
- CXCL13
- IL-6

MRI biomarkers:

- Mean number of T1 Gd-enhanced lesions
- Mean number of new and/or enlarging T2 lesions
- Mean T2 lesion volume
- Mean Regional or total brain volume
- Mean number of leptomeningeal-enhancing regions

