2.3 DETERMINATION OF SAMPLE SIZE

The sample size calculations for this study are based on the assumed reduction from baseline in NfL at Weeks 24 and 52 combined (Arms 2 and 3) in the RMS cohort. Other biomarker measures are not considered for power determination.

Assuming (a) a 30% reduction from pre-treatment NfL (mean [SD] = 860 pg/mL [780 pg/mL]) to posttreatment NfL (mean [SD] = 602 pg/mL [310 pg/mL]) and a correlation coefficient of 0.6, resulting in an SD of 643 pg/mL for the change from pre- to post-treatment, and (b) a desired power of 80% with a Type 1 error of 5%, a sample size of 51 patients is required, with approximately 25 patients in Arm 2 and 26 patients in Arm 3.

This is the first study to explore the impact of ocrelizumab on CSF B-cell count. In a study by Piccio et al. (2010), the rate of undetectable B cells in CSF was 74% (21/26) after 24–30 weeks of rituximab as an add-on to immunomodulatory therapy. Based on this information and a sample size of 51 patients (Arm 2 and 3 combined), the expected 95% CI for the CSF Bcell undetectable rate will be: (0.61, 0.85).

In the RMS cohort, 15 patients will be included in Arm 1 to explore the possible reduction in NfL at Week 12 post-treatment and 15 patients will be assigned to the delayed start RMS control arm (Arm 4). At least 15 patients will be recruited to the PPMS cohort. The above sample sizes are not based on statistical considerations and are meant to help explore the changes in biomarkers and generate hypotheses for future studies.

Based on the above, the total sample size for this study will be at least 96 patients. The sample size will be increased by approximately 10% in order to account for potential missing post-treatment CSF information; therefore, the number of patients to be enrolled in the RMS cohort will be $N = 88$ (Arm 1: 16 patients, Arm 2: 28 patients, Arm 3: 28 patients, and Arm 4: 16 patients).

The PPMS cohort will enroll at least 16 patients, and additional PPMS patients were allowed to enroll to collect more information on biomarkers. The total sample size of the PPMS cohort may approximate 30 patients. Therefore, the total number of patients to be enrolled is at least 104, and may reach approximately 130 patients.

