4.1.1 Intent-to-treat (ITT) Population

The ITT population is defined as all patients enrolled in the study who received at least one dose of Ocrevus. Summaries such as patient disposition and baseline biomarkers will be performed on the ITT population. Summaries of all primary and exploratory endpoints will also be performed using the ITT population.

Patients in this study were randomized/assigned into arms to take the 2nd LP at different timings, while receiving the same treatment. In order to summarize the effect of ocrelizumab on biomarkers over time more accurately, patients will be summarized by the actual “arm” depending on when the patient actually received the 2nd LP.

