4.4.2 Exploratory Endpoints

4.4.2.1 Summaries of Exploratory Endpoints Over Time

For RMS patients in Arm 4, values at pre-treatment baseline and treatment baseline, and change and percent change from treatment baseline to post-baseline visits will be summarized.

For RMS patients in arms 1-3 and PPMS patient arm, CSF biomarker endpoints, blood biomarker endpoints and MRI biomarker endpoints stated in Section 2.2.2 will be summarized over time following the same rule as the primary efficacy endpoint, as stated in Section 4.4.1. The median (IQR) value of CSF and blood biomarkers at pre-treatment baseline, treatment baseline and post-baseline visits will be plotted over time and color coded by each arm. Scatter points of data will be laid over the median (IQR) plot for blood NfL level, CD19+ B cell and CD3+ T cell numbers.

Mean (SD) of MRI biomarker endpoints will be summarized over time.

For blood biomarkers, patient arms will also be pooled to look at the effect of ocrelizumab over time.

4.4.2.2 Comparison between Arm 1 and Arm 4

For patients in Arm 4, changes from pre-treatment baseline to treatment baseline will be compared to Arm 1 change from treatment baseline to Week 12 through an ANCOVA model adjusting for baseline DMT status (DMT naïve vs. DMT experienced) and baseline biomarker level for the following endpoints:

- CSF CD19+ B cell, CD3+ T cell and NfL
- Blood CD19+ B cell, CD3+ T cell and NfL

If data are highly skewed, ANCOVA model will be based on percent changes.

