In the RMS cohort, 15 patients will be included in Arm 1 to explore the possible reduction in NfL at Week 12 post-treatment and 15 patients will be assigned to the delayed start RMS control arm (Arm 4). *At least 15 patients will be recruited to the PPMS cohort. The above sample sizes are not based on statistical considerations and are meant to help explore the changes in biomarkers and generate hypotheses for future studies.*

Based on the above, the total sample size for this study will be *at least* 96 patients. The sample size will be increased by approximately 10% in order to account for potential missing post-treatment CSF information; therefore, the number of patients to be enrolled in the RMS cohort will be 88 (Arm 1: 16 patients, Arm 2: 28 patients, Arm 3: 28 patients, and Arm 4: 16 patients), and *at least* 16 in the PPMS cohort. Therefore, the total number of patients to be enrolled is *at least* 104; *however, the addition of patients to the PPMS cohort would allow for even more detailed information on biomarkers.*

Interim Analyses

For the RMS patients, interim analysis may be performed when approximately 50% of patients have had their second LP. For the PPMS patients, interim analyses may be performed after approximately 50% of patients have had their baseline LP and/or approximately 50% have had their second LP.

APPENDIX 2
VISIT WINDOWING FOR MAIN TREATMENT AND LTE PERIOD

Visit window for vital sign and blood biomarkers (Arm 1-4 & PPMS):

Report Visit Label	Nominal study days (from baseline)	Visit window (in terms of study days from baseline)	Notes
Week -12 (Arm 4)	-84	< -14	
Baseline (Arm 1-3 & PPMS)	1	<=1	ANLFL for the record most close to day 1 if there are multiple records in the window
Baseline (Arm 4)	1	-14 - 1	Give two week window for baseline
Week 3	21	2<= and <=53	Window is from Day 2 until Week 7.5+0.5 day
Week 12	84	54<= and <=126	Window is from Week 7.5+1.5 day until Week 18
Week 24	168	127<= and <=210	Window is from Week 18+1 day until Week 30
Week 36	252	211<= and <=294	Window is from Week 30+1 day until Week 42
Week 48	336	295<= and <=350	Window is from Week 42+1 day until Week 50
Week 52	364	351 - < LTE Day 1 (if entered LTE) 351 – patient end of main study date (if not entered LTE)	Window is from Week 50+1 day until end of main study date
Week 96	672	LTE Day 1 - <=840	Window is from LTE Day 1 to Week 120
Week 144	1008	>=841 and <=1,176	Window is from Week 120+1 day until Week 168

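### The Arm 4 comparison of blood NfL, CD19+ and CD3+ uses Arm 1 alone, although Arms 2 and 3 give the same Week 1 to Week 12 blood change on the same treatment; pooling would be a cheap gain in precision, mainly for NfL

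*SAP*

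**What the plan says.** SAP 2.2.2 defines the Arm 4 endpoints as "Change from first LP to second LP comparing Arm 4 to Arm 1 in" six quantities: NfL, CD19+ B cells and CD3+ T cells, each in CSF and in blood. SAP 4.4.2.2 carries this out. Arm 4's change from Week -12 to Week 1 "will be compared to Arm 1 change from treatment baseline to Week 12 through an ANCOVA model", adjusted for prior-therapy status and baseline level. The blood endpoints in the model are listed as "Blood CD19+ B cell, CD3+ T cell and NfL".

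On what the arms have in common, SAP 4.1.1 states: "Patients in this study were randomized/assigned into arms to take the 2nd LP at different timings, while receiving the same treatment". The footnote to Protocol Figure 1, which covers Arms 1-3 together, says: "Biomarkers will be assessed via blood draws at Week 1 (pre-dose Day 1), Week 3 (pre-dose Day 15), and at timepoints noted" from Week 12 onward. Protocol Appendix 1 is a single schedule for the three arms. It marks the TBNK panel, plasma and serum at Weeks 1 and 12 with no restriction by arm. SAP Appendix 2 has one table, headed "Visit window for vital sign and blood biomarkers (Arm 1-4 & PPMS"), with one Week 12 window (Days 54 to 126).

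The SAP does pool blood data elsewhere. Section 4.4.2.1 says: "For blood biomarkers, patient arms will also be pooled to look at the effect of ocrelizumab over time". That covers summaries over time. Neither 4.4.2.2 nor the sensitivity analyses in 4.4.3 extend pooling to the Arm 4 comparison.

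**The concern.** Arm 4 exists because Protocol 3.1 warns that biomarkers may drift back towards their mean, and that this could be misread as a drug effect. The contrast in SAP 4.4.2.2 is the only controlled comparison planned for blood biomarkers. Its precision is limited by two groups of about 16.

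For CSF nothing can be done about the treated side: among Arms 1-3, only Arm 1 has a scheduled Week 12 puncture. For blood, the assignment to Arm 1, 2 or 3 settles only when the second puncture happens. The Week 1 to Week 12 blood change is the same quantity in all three arms, measured at the same visits and sorted into the same window. Leaving Arms 2 and 3 out makes the intervals wider than the collected data require.

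**Working it through.** **Inputs.** Planned enrolment is given in SAP 2.3: "Arm 1: 16 patients, Arm 2: 28 patients, Arm 3: 28 patients, and Arm 4: 16 patients". So Arms 1-3 together are 16 + 28 + 28 = 72, and Arms 2-3 are 28 + 28 = 56. The evaluable targets in the same section are 15 for Arm 1, 51 for Arms 2 and 3 together, and 15 for Arm 4, so Arms 1-3 give 15 + 51 = 66. Tests are two-sided at 5%.

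**The plan's own figure.** SAP 2.3 gives no precision or power for Arm 1 versus Arm 4. Its one sample-size figure, 51 for the paired CSF NfL change, reproduces. The SD of change is √(780² + 310² − 2·0.6·780·310) = 643.7, the difference is 860 − 602 = 258, and a paired t-test with 80% power needs 51 patients (49 by the normal approximation).

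**Equal SD in both groups (assumed).** The standard error of a difference, in SD units, is √(1/n₁ + 1/n₂).

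- Planned, 16 versus 16: √(2/16) = 0.354
- Pooled, 72 versus 16: √(1/72 + 1/16) = 0.276
- Ratio: 0.354/0.276 = 1.28, so the planned intervals are 28% wider
- Effective size per group: 2/(1/16 + 1/72) = 26 instead of 16
- With evaluable numbers (15, 15, 66) the ratio is again 1.28
- With t quantiles on the ANCOVA residual degrees of freedom (28 and 84) the half-widths are 0.724 and 0.550 SD, a ratio of 1.32

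For a two-sample t-test, the difference detectable with 80% power falls from 1.02 to 0.78 SD. Power at a true 0.8 SD rises from 59% to 82%.

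**Unequal SD.** Let r be the treated SD of change divided by Arm 4's. The ratio of standard errors is √[(1/16 + r²/16)/(1/16 + r²/72)]. The right-hand column below is the type I error of an ordinary common-variance t-test on 72 versus 16 (simulated, no covariates, normal data, 40,000 runs per setting, nominal 5%).

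| r (assumed) | Planned interval wider by | Type I error, 72 vs 16, common variance |
|---|---|---|
| 0.25 | 2% | 31% |
| 0.5 | 9% | 19% |
| 0.75 | 18% | 10% |
| 1 | 28% | 5% |
| 1.5 | 47% | about 1% |

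With 16 versus 16, the common-variance test stays between 5% and 6% over the same range. With 72 versus 16 and Welch (unequal-variance) standard errors, it returns to about 5% at every r.

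**The case against.** A reader might infer that the 28% applies equally to all three blood endpoints. The documents do not support that. They give no SD for any blood change. Protocol 5.1.1.1.4 expects rapid depletion of blood CD19+ cells within 14 days, and SAP 4.4 sets values below the quantification limit to half that limit. Both should shrink the treated spread, so for CD19+ a loss of 2% to 9% is plausible. Power is also hardly in question for an effect that is already expected. For CD3+, Protocol 1.2 states that peripheral T-cell numbers are unaffected. The practical gain is mainly for NfL.

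A reader might also infer that the restriction has no rationale. It has one. Protocol 3.1 describes Arm 4 as the control for Arm 1, and the objective in Protocol 2.2 names CSF, blood and MRI together for that pair. Using the same patients keeps the blood and CSF contrasts matched. That is a reason to keep the Arm 1 comparison in the report; it does not require leaving out the pooled one. Protocol 3.1 also says Arm 4 should inform the other treated arms.

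A third tempting reading is that pooling adds no confounding because Arms 1-3 are randomised. SAP 3.1 lets Arm 1 close at its target, after which new patients go only to the remaining arms. If 1:1:1 allocation held until Arm 1 had 16, then 2 × (28 − 16) = 24 of the 56 Arm 2-3 patients could not have been assigned to Arm 1. The arms may therefore not be fully concurrent. Arms are also relabelled by the actual date of the second puncture, although moves among Arms 1-3 leave the pooled group unchanged.

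The strongest technical objection is that putting 72 versus 16 into the planned common-variance ANCOVA can damage validity, as the table shows. This stands, and it determines the form of the fix.

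Finally, the study is exploratory, no primary endpoint or conduct decision depends on this contrast, and Arm 2-3 blood data are still summarised elsewhere. That limits the importance of the point.

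**Conclusion.** The point holds as a cheap improvement. SAP 4.4.2.2 leaves about 56 of 72 treated patients out of the only controlled blood comparison, although they supply the same change on the same treatment. The cost in interval width is about 28% if the SDs are equal. It is about 2% to 18% if the treated SD is a quarter to three quarters of Arm 4's, and about 47% if it is one and a half times as large. All these SD ratios are assumptions. The figures also rest on planned enrolment; the evaluable targets change the equal-SD figure very little.

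The point does not show that the planned comparison is invalid, and pooling would not make the contrast a randomised one. Arm 4 is recruited separately, so selection differences remain however many treated patients are used.

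**What to change.** In SAP 2.2.2 and 4.4.2.2:

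- Keep Arm 1 versus Arm 4 for the three CSF endpoints.
- For blood NfL, CD19+ and CD3+, compare Arm 4 (Week -12 to Week 1) with Arms 1-3 pooled (Week 1 to Week 12), with the same covariates. Use group-specific variances or heteroscedasticity-robust standard errors with a small-sample correction.
- Report Arm 1 versus Arm 4 for blood alongside, to match the CSF comparison and show any discrepancy between Arm 1 and the pool.
- State that pooling addresses precision only and that Arm 4 is not randomised.

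The cost is a few sentences of SAP text and one extra model per blood endpoint. No new patients, visits or samples are needed. The downsides are that the treated group for blood is no longer the same set of patients as for CSF, and that Arms 1-3 may not be fully concurrent if Arm 1 closes early.

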4.4.2.3 Associations Among Biomarker Data

The following associations will be assessed separately for each arm at each scheduled visit:

- CSF with blood NfL, CD19+ B cells, and CD3+ T cells.
- change in CSF NfL levels, CD19+ B cells, CD3+ T cells with changes in T1 Gd-enhanced lesions from treatment baseline to post-baseline scheduled visits for arms 1-3 patients, and from pre-treatment baseline to treatment baseline visit for arm 4 patients.

- brain volume with CSF NfL levels.
- change in CSF NfL levels with new/enlarging T2 Gd-enhanced lesions.
- blood NfL with CSF CD19+B cells, CD3+T cells.
- blood NfL with T1 Gd-enhanced lesions.
- change in blood NfL with new and/or enlarging T2 lesions.

The Spearman's rank correlation coefficient will be used to evaluate the relationship among the levels of biomarkers or between levels of biomarkers and clinical parameters. Baseline values across patient arms may be pooled when appropriate. Scatterplots of the two-by-two associations may also be constructed to aid in the interpretation of the coefficients.

The following associations will be assessed by Mann-Whitney test:

- Baseline CSF NfL in DMT-experienced patients versus DMT-naïve patients.
- Baseline CSF NfL levels in patients with 0, 1 and >1 baseline T1 Gd-enhanced lesions.
- Percent change in CSF NfL in patients having at least one relapse event versus patients without relapse during the study.
- Percent change in CSF NfL in DMT-experienced patients versus DMT-naïve patients.

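### Two blood–MRI correlations are planned by lumbar-puncture arm although Arms 1–3 share treatment and visits; one pooled coefficient per visit should be the main result

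*SAP*

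**What the plan says.** SAP 4.4.2.3 lists seven associations under one rule: "The following associations will be assessed separately for each arm at each scheduled visit". For the measure, Spearman's "rank correlation coefficient will be used to evaluate the relationship among the levels of biomarkers". Five of the seven involve a CSF measurement. The other two do not: "blood NfL with T1 Gd-enhanced lesions" and "change in blood NfL with new and/or enlarging T2 lesions".

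The only allowance for combining arms in that section is "Baseline values across patient arms may be pooled when appropriate", which is discretionary and stops at baseline. No pooled, stratified or combined coefficient is specified for any later visit.

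Elsewhere the SAP treats the arms as alike apart from lumbar-puncture timing. Section 4.1.1 says: "Patients in this study were randomized/assigned into arms to take the 2nd LP at different timings, while receiving the same treatment". Section 4.4.2.1 says: "For blood biomarkers, patient arms will also be pooled to look at the effect of ocrelizumab over time". That second sentence covers time courses of blood markers, not associations.

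**The concern.** The split by arm has a reason only when the arm determines what was measured or how long the patient had been on drug. For the two blood–MRI pairs in Arms 1–3 it determines neither. Protocol Appendix 1 gives Arms 1–3 one schedule, with brain MRI and plasma and serum samples at Weeks 1, 12, 24 and 52. SAP Appendix 2 gives blood and MRI one window table each for all arms. At a given visit the scheduled dosing and time since first dose are therefore the same. Because SAP 4.4 assigns patients to the arm that matches the actual date of the second lumbar puncture, these pairs are divided by the timing of a procedure that they do not use.

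What is at stake is the usefulness of a stated exploratory objective, the correlation of blood or CSF biomarkers with MRI (Protocol 2.2). In the main period, two pairs, three post-baseline visits and three arms give 2 × 3 × 3 = 18 small-sample coefficients where 2 × 3 = 6 pooled ones would answer the question, and no multiplicity correction applies. The same rule reaches the extension, where blood and MRI share visit labels at Weeks 96, 144, 192 and 240.

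**Working it through.** **The plan's own figure.** The documents give no power or precision for any correlation. The only powered figure is the 51 patients for the paired change in CSF NfL (SAP 2.3). It reproduces: SD of change = √(780² + 310² − 2 × 0.6 × 780 × 310) = 643.7 pg/mL, difference 860 − 602 = 258 pg/mL, and a two-sided paired t-test at 5% with n=51 has 80.2% power. It does not bear on the correlations.

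**Inputs.** Enrolled sizes are from SAP 2.3: Arm 1 16, Arm 2 28, Arm 3 28, so Arms 1–3 = 72. Two-sided 5% is from SAP section 4. The documents give no expected blood–MRI correlation; 0.4 is an assumption, and 0.3 and 0.6 are shown as a range.

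**Information kept by one arm.** On the Fisher-z scale the variance is proportional to 1/(n − 3).
- Arm 1: 13/69 = 19% of the pooled information; interval width ratio √(69/13) = 2.3.
- Arm 2 or 3: 25/69 = 36%; width ratio √(69/25) = 1.7.
- With the planned evaluable sizes 15, 25 and 26 (total 66): 12/63 = 19%, 22/63 = 35% and 23/63 = 37%.

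**Intervals and power.** The interval is tanh(atanh r ± 1.96 √((1 + r²/2)/(n − 3))). Power is Φ(atanh r / √(1.06/(n − 3)) − 1.96). For r = 0.4, atanh r = 0.424.

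| n | SE for interval | 95% CI at r = 0.4 | Power at 0.4 | Power at 0.3 | Power at 0.6 |
|---|---|---|---|---|---|
| 16 | √(1.08/13) = 0.288 | (-0.14, 0.76) | 32% | 19% | 68% |
| 28 | √(1.08/25) = 0.208 | (0.02, 0.68) | 54% | 32% | 92% |
| 72 | √(1.08/69) = 0.125 | (0.18, 0.58) | 93% | 70% | over 99% |

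A simulation with 8,000 replicates at an underlying correlation of 0.5 gave standard deviations of Spearman's coefficient of 0.214, 0.156 and 0.095 at n = 16, 28 and 72, which fits these ratios.

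**Sparse Gd lesions.** These figures assume roughly continuous measures. Protocol 1.2.1.2 reports T1 Gd-enhancing lesions reduced by more than 90% against interferon, so most on-treatment counts are likely to be zero. Suppose a share p of patients has any lesion, scored yes or no. The documents give no p, so 3%, 5% and 10% are assumptions. Spearman's coefficient then cannot exceed √(3p(1 − p)), and it is undefined when nobody in the group has a lesion, which has probability (1 − p)ⁿ.

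| p | Maximum coefficient | Undefined, n=16 | Undefined, n=28 | Undefined, n=72 | Simulated power, n=72 (latent correlation 0.42) |
|---|---|---|---|---|---|
| 3% | 0.30 | 61% | 43% | 11% | about 22% |
| 5% | 0.38 | 44% | 24% | 2% | about 34% |
| 10% | 0.52 | 19% | 5% | under 1% | about 51% |

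The 93% therefore does not carry over to on-treatment Gd lesions. Pooling still helps that pair, because the by-arm coefficients are often incalculable.

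**The case against.** The case for leaving the plan alone has several parts.

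- **Most of the list is rightly split.** After baseline, the mandatory CSF sample comes from one randomized RMS arm per visit: Arm 1 at Week 12, Arm 2 at Week 24, Arm 3 at Week 52 (Protocol Table 1). For the five CSF associations the split largely follows data availability, apart from optional punctures. This stands. A reader might infer that these should be pooled or stratified over Arms 1–3 as well; that would mix Weeks 12, 24 and 52, and the documents give no ground for it.
- **Baseline is already covered.** Pooling is allowed there, and baseline is probably the most informative visit for Gd lesions. This stands for that visit; the gap is after baseline.
- **The loss can be exaggerated.** A reader might infer that by-arm analysis discards most of the precision, or that a moderate correlation usually cannot be told from zero. On the standard-error scale Arms 2 and 3 keep about 60% (1/1.66) and Arm 1 about 43% (1/2.30). At n=28 the interval at 0.4 excludes zero and power is 54%. The by-arm estimates could also be combined afterwards, recovering (13 + 25 + 25)/69 = 91% of the information, although the SAP plans no such step.
- **Chance findings.** Keeping by-arm values and adding pooled ones does not reduce the number of coefficients. This stands. The gain is in naming beforehand which ones carry the result.
- **The analyses are exploratory.** No primary endpoint or decision depends on them. This also stands, and it limits the weight of the point.

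**Conclusion.** The point holds for two of the seven associations, after baseline, in RMS Arms 1–3. For those pairs the arm split serves no analytic purpose, and each by-arm estimate keeps 19% or 36% of the pooled information. That ratio depends only on the arm sizes. The intervals and powers also depend on the assumed correlation and on roughly continuous measures; they are plausible at most for the new or enlarging T2 pair and too favourable at every n for on-treatment Gd lesions. Pooling further assumes that the correlation at a given visit does not depend on when the lumbar puncture was done, which randomization and the common treatment support. Arm sizes by actual puncture date may differ somewhat from plan.

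This is a minor improvement to exploratory analyses. It does not show that the by-arm correlations are invalid, and it does not touch the primary endpoints.

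**What to change.** In SAP 4.4.2.3, for the two blood–MRI pairs only, prespecify one Spearman coefficient per scheduled visit, with its 95% interval, pooled over RMS Arms 1–3 as the main result. Keep the by-arm coefficients as supportive displays, so readers can check whether they look alike. For Gd lesions, also report how many patients have any lesion at each visit, because that number governs what the coefficient can show.

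Keep PPMS separate (different disease course and a different infusion schedule in the main period), and keep Arm 4's untreated interval from Week -12 to Week 1 separate. Leave the post-treatment CSF associations as they are.

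The cost is a few extra output lines and no new data. Making the change before the analysis also avoids a decision to pool after the by-arm results have been seen.
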